Appendix 9. Prohibited Hepatotoxic Agents

All other hepatotoxic agents will be left to the discretion of the PI. There should be clear documentation in the subject records of Investigator approval of use. For subjects who have been on stable therapy with no related hepatotoxicity, the MM may be contacted to assess the medical context and eligibility of the subject.

*Prohibited Hepatotoxic Concomitant Medications	
Generic Name	Drug Class/Common Use
Acetaminophen > 3000 mg/day	Analgesic/Antipyretic
Albendazole	Anthelmintics (parasitic infections)
Amiodarone	Antiarrhythmic
Amodiaquine,	Antimalarial
Azathioprine/6-Mercaptopurine	Antineoplastic/Antirheumatic, autoimmune
Buspirone	Sedatives, hypnotics, Psychoactive drug – for anxiety
Busulfan	Antineoplastic/Alkylating, cancer
Carbamazepine	Anticonvulsant
Chemotherapies	
Chlorpromazine	GI, antipsychotic
Dantrolene	Muscle relaxant
Didanosine	Antiviral
Dimethyl Fumarate	For MS
Disulfiram	Alcohol Deterrents
Dronedarone	Antiarrhythmic (AFib/flutter)
Efavirenz	Antiviral
Fenofibrate	Anti-lipemic Hypertriglyceridemia, hypercholesterolemia
Floxuridine	Antineoplastic, cancer
Flutamide	Antineoplastic, nonsteroidal antiandrogen (NSAA)
Glatiramer acetate	For MS
Gold Salts	Antirheumatic, RA
Halothane	Anesthetics for surgery
Hydralazine	Antihypertensive
Infliximab	Antirheumatic, Dermatologic, GI
Interferon alpha	Antiviral
Interferon beta	MS
Isoniazid	Anti TB
Methotrexate	Antineoplastic, Antirheumatic, Dermatologic
Methyldopa	Antihypertensive
Nefazodone	antidepressant
Nevirapine	Anti-viral (HIV/AIDS therapy)
Nimesulide	NSAID – COX-2
Nitrofurantoin	Anti-infective, urinary (antibiotic)
Norethisterone	For menstrual issues
Phenytoin	anticonvulsant
Pirfenidone	Pulmonary fibrosis
Propylthiouracil	Antithyroid
Pyrazinamide	Anti TB
Quinidine	Antiarrhythmic
Rifampin	Anti TB
Sulfasalazine	Anti-infective (DMARD, antibiotic)
Suramin	Injectable – antiprotozoal agent
Thioguanine	Antineoplastic/Antirheumatic,
Ticlopidine	Antithrombotic, platelet inhibitor
Valproate	Anticonvulsant (epilepsy), mood stabilizer (Bipolar)

# **GLOSSARY OF ABBREVIATIONS**

Abbreviation	Definition	
ADA	Antidrug antibody	
AE	Adverse event	
ALP	Alkaline phosphatase	
ALT	Alanine aminotransferase	
ANCOVA	Analysis of covariance	
ANOVA	Analysis of variance	
AST	Aspartate transaminase	
ATC	Anatomical-Therapeutic-Chemical	
BMI	Body mass index	
C4	7-alpha-hydroxy-4 cholesten-3-one	
CI	Confidence interval	
CMH	Cochran-Mantel-Haenszel	
CRN	Clinical Research Network	
CTCAE	Common Terminology Criteria for Adverse Events	
DNA	Deoxyribonucleic acid	
ECG	Electrocardiogram	
ELF	Enhanced liver fibrosis	
eCRF	Electronic case report form	
EOS	End of study	
EOT	End of treatment	
FAS	Full analysis set	
GGT	Gamma-glutamyl transferase	
HDL-C	High density lipoprotein cholesterol	
HOMA IR	Homeostasis model assessment-estimated insulin resistance	
ITT	Intent to treat	
IxRS	Interactive Web/Voice Response System	
LDL-C	Low density lipoprotein cholesterol	
LFC	Liver fat content	
LISSA	Local injection-site symptom assessment	
MAR	Missing at random	
MCP-Mod	Multiple comparison procedure – modelling	
MedDRA	Medical Dictionary for Regulatory Activities	

Abbreviation	Definition
MI	Multiple imputation
MRI PDFF	magnetic resonance imaging proton density fat fraction
NAB	Neutralizing antibody
NAFLD	Nonalcoholic fatty liver disease
NAS	NAFLD activity score
NASH	Nonalcoholic steatohepatitis
NCI	National Cancer Institute
NIH	National Institutes of Health
PK	Pharmacokinetic
PP	Per protocol
Pro-C3	N-terminal Type III collagen
PT	Preferred term
SAE	Serious adverse event
SAP	Statistical analysis plan
SAS	Statistical Analysis System
SC	Subcutaneous
SD	Standard deviation
SOC	System organ class
TEAE	Treatment emergent adverse event
WHO	World Health Organization

#### 1. Introduction

This Statistical Analysis Plan (SAP) provides the details of the statistical analyses to be performed for NGM Biopharmaceuticals clinical study 18-0108 (ALPINE 2/3) entitled "A Phase 2b, Randomized, Double-blind, Placebo-controlled, Multi-center Study to Evaluate the Efficacy, Safety, and Tolerability of Three Doses of Aldafermin Administered for 24 Weeks for the Treatment of Histologically Confirmed Nonalcoholic Steatohepatitis (NASH)".

There will be one database lock after all study subjects have exited study and all data clarifications have been resolved.

## 1.1 Primary Study Objectives and Design

The primary objectives of this study are to evaluate the efficacy, safety and tolerability of Aldafermin administered for 24 weeks of treatment of histologically confirmed NASH compared to placebo.

This is a multiple center evaluation of Aldafermin administered for 24 weeks as a daily subcutaneous (SC) injection in a randomized, double-blind, placebo-controlled study in subjects with histologically confirmed NASH. Approximately 152 subjects, of which no more than 15% (approximately 22 subjects) will be self-identified Asian subjects, will be randomized at approximately 40 sites in the United States (US).

Subjects to be studied will have histologically confirmed NASH as defined by the National Institutes of Health (NIH) NASH Clinical Research Network (CRN) and determined by a qualified central pathologist's reading. Subjects must have a nonalcoholic fatty liver disease (NAFLD) activity score (NAS) of at least 4, with a minimum of 1 point in each of the three components (steatosis, inflammation and ballooning), along with the presence of either Stage 2 or 3 fibrosis. Subjects with no (Stage 0) or minimal (Stage 1) fibrosis and cirrhosis (Stage 4) will be excluded from this study. Subjects will undergo magnetic resonance imaging (MRI) during the Screening period, which must demonstrate ≥8% total liver fat content (LFC) by MRI proton density fat fraction (MRI PDFF).

On Day 1, eligible subjects will be randomized into one of the four treatment groups (Aldafermin 0.3 mg, Aldafermin 1 mg, Aldafermin 3 mg, or placebo) in a 1:1:1:1 ratio (n=38 subjects in each treatment group). The randomization will be stratified by baseline stage of fibrosis

[figure not shown]
The first dose of Aldafermin (Day 1) and doses at Weeks 2, 4, 8, 12, 18, and 24 study visits will be self administered in the clinic, with all other daily doses through Week 24 self administered daily at a similar time at home. Subjects will return to the clinic on Weeks 2, 4, 8, 12, and 18 for on treatment assessments and to receive Aldafermin study drug kits.

Low density lipoprotein cholesterol (LDL-C) will be evaluated at Weeks 2, 4, 8, 12 and 18 in all subjects for possible increases in lipid levels associated with Aldafermin administration. In statin naïve subjects, rosuvastatin will be started in subjects meeting specific LDL-C level criteria at Week 2. In statin experienced subjects, rosuvastatin (10mg OD in non-Asians and 5mg in Asians) will be started at Week 2. Rosuvastatin and matched placebo are over encapsulated to maintain the blind at the sites and with the sponsor study teams. Initiation and ongoing dose adjustments of rosuvastatin/matched placebo will be managed by an unblinded third-party medical monitor and through the ....... The sponsor and study sites will be blinded to LDL-C values and the specific rosuvastatin dosing decisions as outlined in Section 9.4.14 of the protocol. Subjects who have not achieved an adequate response or cannot tolerate rosuvastatin as defined in Section 9.4.14 of the protocol will be considered for the addition of ezetimibe as second-line lipid management therapy. Ezetimibe 10 mg tablets can be administered with or without food at the same time as rosuvastatin and Aldafermin or as monotherapy. Subjects whose LDL-C values are not adequately managed by their maximum tolerated rosuvastatin dose plus ezetimibe will be discontinued from study and an early withdrawal study visit will be completed. The follow-up/end-of-study (EOS) visit should be scheduled for 6 weeks after the early withdrawal study visit.

Rosuvastatin or matching placebo will be dispensed at each study visit through Week 18 (statin-naïve) or Week 24 (statin experienced). If the subject is taking over-encapsulated rosuvastatin or matched placebo, evaluate tolerability and continue therapy to Week 24 if statin naïve or Week 30 if statin experienced.

All subjects will return to the clinic at Week 25 for post-treatment LDL-C assessment. Subjects who have an LDL-C value of >100 mg/dL and > 15 mg/dL above their Day 1 value at Week 25 will be re-assessed at Week 30. Subjects who have an LDL-C value of > 100 mg/dL and >15 mg/dL above their Day 1 value at Week 30 will have an additional 4-week follow-up visit to confirm their LDL-C value is  $\leq$  100 mg/dL or  $\leq$  15 mg/dL above their Day 1 value.

The study visit at Week 24 will be the Aldafermin end-of-treatment (EOT) clinic visit and subjects will return to the clinic at Weeks 25 and 30 (or at 1 and 6 weeks after last dose of Aldafermin) for a post-treatment response and EOS follow-up visits. Subjects are required to undergo MRI PDFF on Screening Day -28 and at Weeks 12, 24/Early Withdrawal (EOT), and 30 (EOS) visits.

## 1.2 Secondary and Other Objectives

The secondary objectives of this study are to evaluate the effect of Aldafermin on the pharmacokinetics, biomarkers of target engagement, fibrogenesis, and imaging.

## 1.3 Sample Size

The sample size for this study is determined based on power simulations for the dose-response testing for the primary efficacy endpoint – the liver fibrosis response (Section 5.1.1). The simulations were originally performed using a generalized MCP-Mod (multiple comparison procedure - modelling) approach (Pinheiro 2014) and those results are presented in the study protocol. The simulation results (Table 1) in this SAP were obtained using a different MCP-Mod approach (Klingenberg 2009) as this approach will be used for both dose-response testing and estimation for the primary efficacy endpoint.

The assumptions about the liver fibrosis response rate for the 4 treatment groups are the same as those in the protocol. Specifically, assuming that the liver fibrosis response rate is 15% for placebo and 50% for Aldafermin 3mg, respectively, it is demonstrated that a total sample size of 152 subjects (38 subjects per treatment group) will provide at least 85% power to detect a positive dose-response trend (i.e., an upward slope) at the 5% significance level (two-sided) under 6 different dose-response scenarios as shown in Table 1 (the last 6 rows). To account for potential premature discontinuation of the study subjects, a 15% drop-out rate at Week 24 is also assumed in all these simulations (i.e., only 32 subjects per group were used in these simulations).

In addition, simulations were also performed under the assumption of no dose effect (i.e., response rate=15% for all 4 treatment groups) to assess the type I error rate control of the MCP-Mod approach (first row in Table 1).

Table 1. Power Simulations for Dose-Response Testing

Liver Fibrosis Response Rate				
Placebo	Aldafermin 0.3 mg	Aldafermin 1 mg	Aldafermin 3 mg	Power
15%	15%	15%	15%	5%
15%	16%	19%	50%	92%
15%	18%	30%	50%	90%
15%	20%	42%	50%	93%
15%	32%	39%	50%	85%
15%	36%	45%	50%	87%
15%	43%	48%	50%	90%

## 2. Analysis Sets and Data Conventions

## 2.1 Analysis Sets

Subjects in this study will be analyzed using the following analysis sets:

- Intent-to-Treat Analysis Set: All randomized subjects will be included in the Intent-to-Treat (ITT) analysis set. The ITT analysis set will be used for the primary and secondary efficacy analyses and will be based on the randomized treatment if it differs from the actual treatment received.
- Safety Analysis Set: All subjects who receive at least one dose (full or partial) of study drug will be included in the safety analysis set. All safety endpoints will be summarized using the safety analysis set and will be based on the actual treatment received if it differs from the randomized treatment.
- Full Analysis Set: All randomized subjects who receive at least one dose (full or partial) of study drug and have at least one valid, non-missing post-dose efficacy/PD value will be included in the full analysis set (FAS). The FAS will be used for sensitivity analyses to support the ITT analyses and will be based on the randomized treatment if it differs from the actual treatment received.
- Per Protocol Analysis Set: The Per Protocol (PP) analysis set is a subset of the FAS and will include subjects who have at least one valid, non-missing baseline and post-dose liver biopsy results and do not have protocol deviations or inter-current events that impact the liver biopsy assessments. The PP analysis set will be used for sensitivity analyses to support the ITT analyses, and this analysis set will be determined by the study team prior to the database lock or unblinding.

#### 2.2 Data Conventions

The following data conventions will be used for all analyses described in this SAP.

- All subject-level data will be provided in data listings, unless stated otherwise.
- Study day will be calculated as:
  - o visit date first dose date, for screening visits;
  - o visit date first dose date + 1, for post-baseline/treatment visits.
- Baseline value will be defined as the last available, valid, non-missing assessment reported before the start of first study drug administration. The randomization date (and time, if available) will be used if the study drug start date is missing or not available for any reason.
- Change from baseline (change) is calculated as follow-up baseline. Percent (or relative) change from baseline (percent/relative change) is calculated as 100 × (change from baseline/baseline).
- Descriptive statistics including the number of non-missing observations (n), arithmetic mean (mean), standard deviation (SD), median, minimum (min), and maximum (max) will be presented for continuous endpoints. Frequency and percentage distribution will be presented for categorical endpoints. Kaplan-Meier estimates will be presented for time-to-event endpoints if applicable.
- Continuous endpoints will be analyzed using an analysis of variance (ANOVA) or analysis of covariance (ANCOVA) model. Ordinal categorical endpoints will be analyzed using a Wilcoxon rank-sum test. Nominal categorical endpoints will be analyzed using a Pearson's Chi-square test or Cochran-Mantel-Haenszel (CMH) test (A Fisher's exact test will be used if ≥ 25% of the cells have expected counts < 5). Time-to-event endpoints will be analyzed using a (stratified) log-rank test and Cox's proportional hazards model.

- Type III sums of squares will be used for all ANOVA and ANCOVA models.

- The level of statistical significance used for all statistical tests will be 0.05, unless stated otherwise. Statistical hypotheses for the primary efficacy analyses and the associated sensitivity analyses will be tested for statistical significance with two-sided alternatives, and one-sided alternatives will be used for all secondary and other efficacy analyses. All confidence intervals (CIs) will be two-sided, unless stated otherwise.
- Data from unscheduled visits will be presented in data listings, but will not be used for statistical analysis/summaries.
- Missing data for selected histological endpoints (e.g., primary and secondary) will be imputed using the methods as described in Section 5. Missing or incomplete dates for adverse events (AEs) and medications may be imputed as needed (e.g., to determine treatment emergence or distinguish between prior and concomitant medications) based on programming conventions. No imputations will be performed for missing or incomplete data of other types and, in this case, analyses will be performed based on the observed data only.

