iii. Adverse event of muscle symptoms (e.g., myalgia, pain, or weakness) or elevated creatine kinase:

A sample will be collected for assessment of CK within 48-72 hours, and CK assessment will be repeated if needed (refer to [Appendix 5](#)). At Weeks 12 and 24, the creatine kinase (CK) level will be compared to the subject's baseline level.

- If CK level is $\leq 3x$ baseline, subject will continue on aldafermin and over-encapsulated rosuvastatin.
- If CK level is $> 3x$ baseline, CK will be repeated within 48 - 72 hours and aldafermin and rosuvastatin will be held:
 - If CK is $\leq 3x$ baseline, subject can re-start on aldafermin and rosuvastatin based on the investigator's judgement.
 - If CK is $> 3x$ and $< 5x$ baseline, repeat CK levels within 48 - 72 hours while aldafermin and rosuvastatin on hold.
 - If CK is $\geq 5x$ baseline, aldafermin and rosuvastatin will be discontinued.

Upon repeat testing for subjects previously with CK $> 3x$ but $< 5x$ baseline:

- If CK is $\leq 3x$ baseline, subject can re-start on aldafermin and rosuvastatin based on the investigator's judgement.
- If CK level is $> 3x$ baseline, subject will discontinue aldafermin and rosuvastatin.

iv. Laboratory value(s) indicative of DILI:

- a) Elevation of AST or ALT $> 2x$ above subject-specific baseline value (calculated using the average of the Day -42, Day -28 and the Day 1 values) and total bilirubin $> 1.5 \times$ subject-specific baseline value, repeat testing of ALT, AST, and bilirubin must be performed within 48 - 72 hours. If there are persistent elevations (AST or ALT $> 2x$ baseline or TBL $> 1.5x$ baseline values) upon repeat testing, then close observation (testing and physical examination 2 - 3 times per week) should be implemented and discontinuation of aldafermin and rosuvastatin should be considered (see b [below](#)).
- b) A decision to discontinue or temporarily interrupt the study drug will be considered based on factors that include how much higher than baseline ALT and AST were relative to the upper limit of normal (ULN) and how much the on study ALT and AST levels have increased relative to baseline, in addition to whether there is concomitant elevation of bilirubin or INR. Aldafermin and rosuvastatin will be discontinued or temporarily interrupted as follows:
 - If baseline measurements (BLM) were $< 2x$ ULN, discontinue if ALT or AST increases to $> 5x$ BLM
 - If BLM $\geq 2x$ ULN but $< 5x$ ULN, discontinue if ALT or AST increases to $> 3x$ BLM

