9.1 Schedule of Study Procedures

The Schedule of Study Procedures is shown in [Table 4](#). The visits should occur as close to the intended dates as possible. However, Weeks 2 and 4 will have a visit window of ± 3 days. Weeks 8, 12, 18, and 24 will have a visit window of ± 7 days. Week 25 will have a visit window of $+3$ days, and Week 30 will have a visit window of ± 7 days. Subjects attending any visits out of windows from Day 1 to Week 24/Early Withdrawal (EOT) visit should be brought back into compliance with the overall study-visit schedule as soon as possible thereafter. Subjects will return to the clinic at Week 25 and Week 30 (1 and 6 weeks after last dose) for a post-treatment response and EOS follow-up visits, respectively.

Subjects who have an LDL-C value of > 100 mg/dL and > 15 mg/dL above their Day 1 value at Week 25 will need to be re-assessed at Week 30. Subjects who have an LDL-C value of > 100 mg/dL and > 15 mg/dL above their Day 1 value at Week 30 will have an additional 4- week follow up visit to confirm their LDL-C value is ≤ 100 mg/dL or ≤ 15 mg/dL above their Day 1 value. Subjects will continue to be followed until their LDL-C value is ≤ 100 mg/dL or ≤ 15 mg/dL above their Day 1 value. Subjects whose LDL-C values are not adequately managed by their maximum tolerated rosuvastatin dose plus ezetimibe will be discontinued from study and an early withdrawal study visit will be completed. The follow up/EOS visit should be scheduled for 6 weeks after the early withdrawal study visit.

Table 4. Schedule of Study Procedures

Study Procedure	(Screening) ^b	D -42	D -28 to -1	D1	W2	W4	W8	W12	W18	W 24/EW (EOT)	W25 (Post-Tx)	W30 (EOS)
Visit Window (Days) ^a					± 3	± 3	± 7	± 7	± 7	± 7	+3	± 7
Informed consent		X										
Demographics		X										
Medical history		X										
Smoking History		X										
Inclusion/exclusion criteria		X		X								
Height		X										
Body weight, BMI, waist circumference		X		X				X		X		X
		■		■	■	■	■	■	■	■	■	■
Alcohol Consumption ^c		X										
12-lead ECG		X		X				X		X		X
Vital signs		X		X	X	X	X	X	X	X		X
Central read of locally performed historical biopsy slides, if available		X										
MRI-PDFF ^d				X				X		X		X
Liver biopsy ^e				X						X		
				■								
Prior and concomitant medications		X	X	X	X	X	X	X	X	X	X	X
Adverse events ^f		X	X	X	X	X	X	X	X	X	X	X
LISSA evaluations				X	X	X	X	X	X	X		
Chemistry (fasted \geq 10 hrs)		X ^h	X ^h	X ^{g,h}	X ^g	X ^g	X ^g	X ^{g,h}	X ^g	X ^{g,h}	X ^g	X ^g

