^c During screening, sites will complete; i) AUDIT-C alcohol consumption questionnaire and, ii) document subject- reported alcohol consumption to confirm whether amounts are within protocol defined limits (refer to exclusion criterion #19)

^d Screening Day -28 MRI-PDFF (includes [REDACTED]) will serve as baseline for efficacy endpoint analysis. The Screening MRI result is valid for up to 8 weeks and may be used for a subject who is re-screened within that time frame. [REDACTED]

^e All subjects are required to have a liver biopsy result at Screening and additional liver biopsy at Week 24. A Screening liver biopsy will be performed only in subjects who do not have a historical biopsy available within 6 months of Screening.

^f Adverse events will be monitored and recorded from subject signing informed consent through follow-up.

^g Serum chemistry will include ALT, AST, ALP, bicarbonate, bilirubin (direct and total), BUN, calcium, chloride, creatinine, CK, GGT, glucose, HDL, LDL, lipase, phosphate, potassium, proteins (albumin, total protein), sodium, total cholesterol, and TG. Lab results for ALT, AST, total cholesterol, LDL, HDL, and triglycerides are blinded to the site and sponsor from Week 2 onward.

^h Creatine Kinase will be collected at Day -42, Day 1 and Week 12, and Week 24.

ⁱ A serum pregnancy test will be performed on all female subjects of childbearing potential at Day -42, -28 Screening visits and Day 1 (pre-dose). A urine pregnancy test will be performed on all female subjects of childbearing potential at Weeks 4, 12, 24, and 30. If the urine pregnancy test is positive, a serum pregnancy test will be performed to confirm

results.

^j Urine drug and alcohol screens may be repeated during treatment for subjects suspected of excessive alcohol intake or to rule out association with a safety event

^k C4 and bile acid testing will be collected at Day 1 and Weeks 2, 4, 8, 12, 18, 24, 25 and 30. In addition, for subjects participating in the optional PK sub-study, additional C4 will be tested at the same timepoints as the PK blood sample collections: Day 1 and Week 24 at pre-dose, and post-dose at 0.5, 1, 2, 4, 6, 8, 12, and 24 hours.

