## 5.1.6 Sensitivity Analyses

# 5.2 Secondary Efficacy Analyses

Secondary efficacy analyses will include treatment group comparisons of the fibrosis response (the primary efficacy endpoint) between each Aldafermin dose and placebo as well as the analyses of the following secondary efficacy endpoints:

- Subjects with resolution of NASH defined as an NAS score of 0 or 1 for inflammation and 0 for ballooning, with no worsening (compared to baseline) of fibrosis as determined by the NASH CRN criteria at Week 24
- Subjects with combined response of fibrosis improvement and NASH resolution, defined as subjects with an improvement in liver fibrosis by ≥ 1 stage with no worsening of steatohepatitis (no increase in NAS for ballooning, inflammation, or steatosis) and resolution of NASH as determined by the NASH CRN criteria at Week 24
- Subjects with improved, no change, and worsening of the following histological assessments at 24 weeks compared to baseline
  - o Fibrosis stage
  - NAS (total score and individual components)
- Subjects with the following changes in LFC by MRI-PDFF at Week 24:
  - o Normalization of LFC (defined as LFC < 5%)
  - $\circ \geq 5\%$  decrease from baseline in LFC
  - $\circ$   $\geq$  30% relative decrease from baseline in LFC
- Change and percent change from baseline to Week 24 in the following:
  - LFC by MRI-PDFF
  - o ALT, AST, total bilirubin, ALP, and gamma glutamyl transpeptidase (GGT)
  - Total cholesterol, high density lipoprotein cholesterol (HDL-C), LDL-C, and triglycerides
  - Lipoprotein particles
  - o Homeostasis model assessment-estimated insulin resistance (HOMA IR)
  - o N-terminal Type III collagen (Pro-C3)
  - o Total ELF Score and individual components (hyaluronic acid, PIIINP, TIMP-1)
  - o 7 alpha hydroxy 4 cholesten 3 one (C4) and serum bile acids (total and individual bile acids)
  - 0
- Subjects with normalization (i.e., values within the normal range) of ALT and AST at Week 24

For binary efficacy endpoints (i.e., responders), treatment group comparisons between each Aldafermin dose and placebo will be performed using the Cochran-Mantel-Haenszel (CMH) test stratified by baseline fibrosis stage. The treatment group difference of the response rates along with the corresponding 90% CI will be provided. The 90% CI will be constructed using the normal approximation method.

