For continuous efficacy endpoints, change and percent change from baseline will be analyzed using an analysis of covariance (ANCOVA) model with effects for treatment, baseline fibrosis stage and baseline outcome value as a covariate. Within the framework of the ANCOVA model, a point estimate of the treatment group difference between each Aldafermin dose and placebo will be provide along with the corresponding one-sided p-value and 90% CI.

All secondary efficacy analyses will be performed using the ITT analysis set. FAS and PP analysis sets will be used as sensitivity analyses. The missing data methods and sensitivity analyses described for the primary efficacy endpoint in Section 5.1 (for ITT and FAS analysis sets) will be used for the following histological endpoints:

- Fibrosis response
- NASH resolution
- Combined response of fibrosis improvement and NASH resolution

All statistical tests for the secondary efficacy analyses will be performed using a one-side test at the significance level of 5%, and no multiplicity adjustment will be made among these secondary efficacy analyses.

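### For five liver analytes the SAP takes one of three scheduled pre-dose values as baseline; averaging them would usually sharpen the secondary ANCOVA, by an amount the documents do not fix

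*SAP*

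**What the plan says.** SAP 2.2 (Data Conventions) sets one baseline rule for every analysis in the plan: "Baseline value will be defined as the last available, valid, non-missing assessment reported before the start of first study drug administration". The visible text makes no exception for liver chemistry.

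SAP 5.2 lists change and percent change to Week 24 in ALT, AST, total bilirubin, ALP and GGT among the secondary endpoints. It analyses them by ANCOVA "with effects for treatment, baseline fibrosis stage and baseline outcome value as a covariate". SAP 2.2 computes change and percent change from the same baseline.

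The schedule in Protocol 9.1 (Table 4) marks fasted chemistry at Day -42, Day -28 and Day 1. Its footnote confirms that all five analytes are in the panel: "Serum chemistry will include ALT, AST, ALP, bicarbonate, bilirubin (direct and total), BUN, calcium, chloride, creatinine, CK, GGT".

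Protocol 8.3, in the rule for suspected drug-induced liver injury, forms a subject-specific baseline that is "calculated using the average of the Day -42, Day -28 and the Day 1 values".

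**The concern.** Liver enzymes vary from draw to draw. A single pre-dose value carries that variation in full, so it predicts the Week 24 value less well than an average of several draws usually would. The ANCOVA then leaves more residual variance and the intervals are wider. Percent change is affected as well, because the same single value is its denominator.

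The protocol already averages liver tests in several places. It allows averaged screening values for the AST and bilirubin entry criteria (Protocol 8.1). It averages Day -42 and Day -28 before comparing a third draw (Protocol 8.2, criterion 6). It averages all three pre-dose values in 8.3. The efficacy analysis uses one.

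At stake is the precision of the secondary liver-chemistry comparisons. Precision matters most at 0.3 mg, where the earlier NASH study saw a smaller fall in ALT than at 1 mg or 3 mg (Protocol 5.2.2).

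**Working it through.** **Inputs from the documents.** There are three scheduled pre-dose draws (Protocol 9.1). The plan has 38 subjects per group, and SAP 1.3 uses 32 after 15% drop-out (38 × 0.85 = 32.3). SAP 2.2 imputes only selected histological endpoints, so the liver-chemistry analyses use observed data and 32 is the relevant number. Secondary tests are one-sided at 5% (SAP 5.2).

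**Not in the documents.** No SD, correlation, power or precision is stated for these analytes, so there is no figure of the plan's own to reproduce. The correlations below are assumptions.

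**Formula.** Let b be the correlation between two pre-dose values and f the correlation of a pre-dose value with Week 24, with equal variances. The residual variance, as a share of the Week 24 variance, is:
- last value only: 1 − f²
- mean of three: 1 − 3f²/(1 + 2b)

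**Case 1: all correlations equal (b = f).**

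| b = f | last value | mean of three | fall in variance |
|---|---|---|---|
| 0.3 | 0.910 | 0.831 | 8.7% |
| 0.5 | 0.750 | 0.625 | 16.7% |
| 0.6 | 0.640 | 0.509 | 20.5% |
| 0.7 | 0.510 | 0.388 | 24.0% |
| 0.8 | 0.360 | 0.262 | 27.4% |
| 0.9 | 0.190 | 0.132 | 30.5% |

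Worked at 0.6: 1 − 0.36 = 0.640; 1 − 1.08/2.2 = 0.509; the ratio is 0.795. The equivalent sample size is 32/0.795, or about 40 evaluable subjects per group instead of 32.

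**Case 2: Week 24 correlates less than the pre-dose values do with each other (f < b).** This is plausible, because Week 24 is months later and on a drug that lowers ALT.
- b = 0.8, f = 0.5: 0.750 against 1 − 0.75/2.6 = 0.712, a fall of 5.1%
- b = 0.7, f = 0.6: 0.640 against 1 − 1.08/2.4 = 0.550, a fall of 14.1%
- b = 0.9, f = 0.4: 0.840 against 1 − 0.48/2.8 = 0.829, a fall of 1.4%

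Over b from 0.7 to 0.9 and f from 0.4 to 0.6 the fall is about 1% to 14%.

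**Case 3: correlation decays with time.** Here the correlation is reliability × exp(−days apart/τ), with draws at days −42, −28, 0 and 168. For reliability 0.7 to 0.9 and τ of 200 to 1,000 days, the result runs from a 1.2% rise (0.9, τ = 200) to an 11.5% fall (0.7, τ = 1,000). The Day 1 value is then closest to Week 24, and averaging in older values can gain nothing.

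**Check by simulation.** A four-arm ANCOVA on change with 32 per group and 3,000 runs gave falls of 16.3%, 18.6%, 24.6% and 28.9% at equal correlations of 0.5, 0.6, 0.7 and 0.8. It gave 3.4% at b = 0.8, f = 0.5. These agree with the formula within simulation error.

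**Mixing the two baselines.** If the mean is the covariate but change is still taken from Day 1, the Day 1 noise stays in the outcome. In the same simulation this raised the variance by 6% to 25% over the last-value analysis.

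**Limit.** The formulas apply to absolute change. Percent change has baseline in its denominator and is not covered by these figures.

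**The case against.** The strongest case for leaving the plan alone has four parts.

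- **The last pre-dose value is a standard and valid baseline.** The randomized comparison is unbiased with either choice. This stands.
- **Screening values were used for selection.** AST and bilirubin limits apply to the Day -42 value or to averaged screening values, and the rise from Day -42 to Day -28 is capped. Averaging those values in adds some regression to the mean to the within-arm changes, and Day 1 is less directly selected. This stands as a small cost. It does not touch the difference between arms.
- **Little hangs on it.** Protocol 12.5.2 calls all secondary efficacy analyses exploratory. With 26 to 27 subjects per arm, the earlier study reported ALT reductions against placebo at p < 0.0001 for 3 mg and 6 mg (Protocol 5.2.2), so precision is unlikely to be the limit at 3 mg. This stands, although it says less about 0.3 mg.
- **The two documents do not conflict.** A reader might infer from Protocol 8.3 that the SAP contradicts the protocol. It does not. The average in 8.3 belongs to an individual-subject safety rule and is applied there to AST, ALT and total bilirubin, not to ALP or GGT. The protocol's efficacy ANCOVA refers only to the baseline outcome value. Where the protocol wants a particular efficacy baseline, it says so, as it does for the Day -28 MRI-PDFF.

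**Conclusion.** The point holds as an optional gain in precision. Two scheduled values per subject for ALT, AST, ALP, GGT and total bilirubin are collected and not used in the efficacy analysis, and averaging would usually narrow the intervals.

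The size cannot be read from the documents. A reader might infer that the plan gives up about a fifth to a quarter of the ANCOVA variance. That figure needs the pre-dose and Week 24 correlations to be equal and to lie at about 0.6 to 0.7, and nothing in the documents supports that. The assumption-dependent range runs from essentially nothing to about 31%. The gain of 40 against 32 evaluable subjects per group applies only at an equal correlation of 0.6.

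The choice is not an error and causes no bias between arms.

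**What to change.** Before unblinding, add one sentence to SAP 2.2. For ALT, AST, ALP, GGT and total bilirubin, the efficacy baseline is the mean of the available scheduled Day -42, Day -28 and Day 1 values, used both as the ANCOVA covariate and as the reference for change and percent change. Keep the last-value baseline as a sensitivity analysis.

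Four limits on the wording:
- Do not pair the mean covariate with change from Day 1.
- Name the five analytes and do not extend the rule to the whole chemistry panel. The panel also contains lipids, and the protocol compares LDL-C with its Day 1 value.
- Say scheduled draws only, because SAP 2.2 keeps unscheduled visits out of the analyses.
- Leave Week 24 normalization of ALT and AST as it is. SAP 5.2 defines it by the normal range, with no baseline involved.

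The cost is one sentence and a derived variable, with no new data, visits or samples. The price is the small regression to the mean in within-arm changes, and a footnote in the tables saying which baseline was used.
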